Currently, most obstetric anesthesiologists use intrathecal morphine for analgesia after cesarean delivery. Based on the pharmacokinetics of morphine and hydromorphone, it would appear that the use of intrathecal hydromorphone for cesarean delivery may result in a similar analgesic profile with fewer side effects. A retrospective study by Rauch (2013) sought to compare the analgesic and side effect profile of intrathecal hydromorphone with local anesthetic vs. intrathecal fentanyl with local anesthetic vs. local anesthetic alone for cesarean section. Pain scores were gathered retrospectively from self-report in response to a nurse's questions. In this study, hydromorphone significantly reduced pain scores in the 0-4 hour range and the 24 hour range as compared to local anesthetic alone or in conjunction with fentanyl. This is the only study in the literature that investigated that role of intrathecal hydromorphone and showed that it provides effective analgesia for cesarean section. There was also a study by Halpern et al. (1996) that compared epidural hydromorphone with epidural morphine for cesarean section. This study found no difference in analgesic effect between the two groups. The Halpern study did identify an earlier peak of pruritus in the hydromorphone group and a later peak in the morphine group. There are, however, no studies that compared intrathecal hydromorphone with intrathecal morphine for cesarean delivery. In order to further characterize the analgesic and side effect profile of intrathecal hydromorphone and determine its future role in obstetric anesthesia, a prospective randomized double blind trial is necessary.

3) Setting of the Human Research

This study will take place at the Mt Sinai Hospital Labor and Delivery Floor. Patients eligible for the trial will be approached by a member of the investigating team after admission to the labor and delivery unit for primary elective cesarean section. These patients will be informed about the trial and consent will be obtained. If the patient does not wish to take place in the trial, she will receive standard anesthetic care.

4) Resources Available to Conduct the Human Research

The study will involve 50 patients scheduled for primary elective cesarean section. The Mt Sinai labor and delivery unit is a very busy unit that performs between 4 and 6 elective cases daily. The obstetricians and nurses on this unit are very cooperative

 MOUNT SINAI SCHOOL OF MEDICINE	Protocol Title:	

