	Principal Investigator:	
	Primary Contact Name/Contact Info	
	Date Revised:	
	Study Number:	

and eager to engage in studies to improve patient care and outcome. In addition, there is a large anesthesia staff during the day that can assist in patient recruitment and data collection.

5) Study Design

This will be a prospective, randomized, double blind study. Patients presenting for primary elective cesarean section will be randomized into two groups. Consent for the study will be obtained in the pre-op area before the patient receives any medication. Group 1 will be the standard morphine group. In this group, the patient's will receive a spinal anesthetic consisting of 1.5cc of 0.75% bupivacaine plus 250mcg of preservative free morphine. Group 2 will be the experimental hydromorphone group. In this group, the patient's will receive a spinal anesthetic consisting of 1.5cc of 0.75% bupivacaine plus 50 mcg hydromorphone. This dose was chosen because it is equipotent to the standard dose of morphine used for cesarean deliveries, which is 250mcg. A second anesthesiologist will draw up the study medication and give the syringe to the investigator so that the investigator is unaware of what is contained in the syringe. The person drawing up the medication does not participate in patient evaluation.

Each patient will receive 500cc of Lactated Ringers within the 15 minutes prior to administration of spinal anesthetic. Each patient will also receive 4mg ondansetron immediately prior to spinal anesthetic.

After performing the spinal anesthetic, each patient will be positioned on the operating room table using standard left uterine displacement. Vitals will be recorded every minute for the first 10 minutes and then every 3 minutes for the remainder of the case. A decrease in BP > 30% of baseline along with a heart rate > 60 or if the patient has symptoms of hypotension (nausea, vomiting, dizziness, or lightheadedness) will be treated with phenylephrine 100 mcg IV boluses and repeated every 1 minute until BP returns to normal. If the HR is below 60, ephedrine will be used in 10mg increments as stated above. Additionally, a bolus of 100cc IV fluid will be given during each hypotensive episode. After the spinal is administered all patients will receive maintenance IVF at a rate of 150cc/hr.

The presence of nausea and vomiting, and pruritus will also be recorded in 5 minute intervals.

 MOUNT SINAI SCHOOL OF MEDICINE	Protocol Title:	
	Principal Investigator:	

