	Primary Contact Name/Contact Info	
	Date Revised:	
	Study Number:	

The dermatomal level of anesthesia will be assessed every 2 minutes until the anesthetic level reaches thoracic level 4 (t-4). We will test for adequate level of anesthesia with a needle testing for the sensation of a pin prick. .

Patient satisfaction will be recorded at the end of the procedure. Patients will be asked to rate their experience on a 1-5 scale as follows. 1-completely dissatisfied, 2-partially dissatisfied, 3-neutral, 4-partially satisfied, 5-completely satisfied.

All patients will have the same post op pain orders as is standard on the labor floor. These include ketorolac 30mg IV every 6 hours. In addition to this, every patient in this study will be given an IV fentanyl PCA (patient controlled analgesia) pump. The settings of the pump will be basal rate of 0, bolus rate of 15mcg, and a lock out of every 8 minutes. This allows a maximum hourly dose of 105mcg. The PCA pumps record how often the patient requested additional analgesia and how much total fentanyl the patient received per hour. The pumps will be queried at the end of 24 hours to record total fentanyl dose can record the total medication administered per hour over a 24 hour period.

The patients will then be followed hourly for the first 4 hours by the investigating team. Pain scores will be obtained using the verbal response scale (VRS). The VRS scale is measured using a score of 0 as no pain and 10 as the worst pain. The presence of nausea and pruritus will also be assessed at these time points. The patients will then be visited again at 6hrs, 12 hrs, and 24 hrs. At these time points, the patients will be asked for pain scores, presence of nausea, vomiting and pruritus.

At 24 hrs, the patients will be evaluated for overall satisfaction with pain control and their anesthetic experience.

a) Recruitment Methods

Every patient that presents for primary elective cesarean section will be a potential candidate for this study. After admission to the labor and delivery floor, the patient will be approached by a member of the investigating team. These patients will be informed about the trial and consent will be obtained. If the patient does not wish to take place in the trial, she will receive standard anesthetic care.

 MOUNT SINAI SCHOOL OF MEDICINE	Protocol Title:	
	Principal Investigator:	
	Primary Contact Name/Contact Info	
	Date Revised:	
	Study Number:	

b) Inclusion and Exclusion Criteria

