Inclusion Criteria for this study:

Elective primary cesarean section; Females age 18-40

Exclusion Criteria:

Emergency cesarean section; Anesthetic other than spinal; History of chronic pain or pre-op opioid use; Allergy to morphine or hydromorphone; BMI>40

c) Number of Subjects

Since there are no prior studies comparing Duramorph to hydromorphone for postoperative analgesia we cannot perform a power analysis to determine the number of patients required. We propose to enroll 20 patients, 10 per group, in a blinded fashion and collect our data as described above. We will then perform an interim analysis of the data to see how much fentanyl is being used in the hydromorphone and morphine group. At that point we will determine the total number of patients required and inform the IRB and update the protocol accordingly. We will not change the protocol in any way after analyzing the data.

d) Study Timelines

Each individual subject will be followed for 24 hours after cesarean section.

We anticipate that we will enroll all subjects within 1 year.

We estimate that this study will be completed 6 months after enrollment of all subjects.

e) Study Endpoints

Each patient will receive a fentanyl pca (patient controlled analgesia) pump in the post anesthesia care unit (pacu). The primary outcome is total dose of fentanyl pca used in 24 hours. This will be a marker for supplemental analgesia needed after the cesarean delivery.

Secondary outcomes include:

1. Time to initial use of pca. We want to understand when the hydromorphone and morphine group will require the first supplemental analgesic.

 MOUNT SINAI SCHOOL OF MEDICINE	Protocol Title:	
	Principal Investigator:	
	Primary Contact Name/Contact Info	
	Date Revised:	
	Study Number:	

2. Time frame of most frequent use of pca. When does each group use the pca most frequently? Between 1-4 hrs, 4-6 hrs, 6-12 hrs, 12-24 hrs? This will help us understand the duration of analgesic effect between hydromorphone and morphine.
3. Pain scores in both groups between the above time frames.
4. Patient satisfaction scores in the above time frames.
5. Assessment of nausea and vomiting and pruritus in the above time frames. This will help us understand the onset and incidence of these side effects among the two groups.

f) Procedures Involved in the Human Research

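### Postoperative nausea, vomiting and pruritus are recorded as presence at visits with no look-back, and vomiting is unlisted at the hourly visits, so the promised onset and incidence by time frame are not secured

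*Combined protocol and SAP*

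**What the plan says.** Section 5(e), Study Endpoints, secondary outcome 5, reads "Assessment of nausea and vomiting and pruritus in the above time frames", and gives the purpose: "This will help us understand the onset and incidence of these side effects among the two groups". The frames, listed under secondary outcome 2, are 1-4, 4-6, 6-12 and 12-24 h.

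Section 5, Study Design, describes three stages of collection:

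- During surgery: "The presence of nausea and vomiting, and pruritus will also be recorded in 5 minute intervals".
- Early after surgery: "The patients will then be followed hourly for the first 4 hours by the investigating team". For side effects at these visits: "The presence of nausea and pruritus will also be assessed at these time points". Vomiting is not named.
- Later: "The patients will then be visited again at 6hrs, 12 hrs, and 24 hrs". Then: "At these time points, the patients will be asked for pain scores, presence of nausea, vomiting and pruritus".

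No sentence says whether presence means now or at any time since the previous visit, and none asks for a start time. Section 5(h) says that a data collection sheet is attached. It is not in the text available here.

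Section 2, Background, reports that an earlier trial of the two drugs given epidurally "did identify an earlier peak of pruritus in the hydromorphone group and a later peak in the morphine group".

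**The concern.** Incidence in an interval needs a question about the whole interval, and onset needs a start time. Presence at a visit, taken at face value, gives point prevalence. After 4 h there is one reading per frame, at its end, so the 12-24 h result would be the symptom status at 24 h. An itch that starts at 14 h and settles by 18 h would be recorded as absent. Vomiting is brief and therefore the symptom least suited to a spot reading. It is also the one left out of the hourly visits.

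The Brief Summary makes the side-effect comparison one of the trial's two questions, beside analgesia. An interval that was never asked about cannot be reliably recovered at analysis.

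**Working it through.** The plan gives no side-effect rate, episode duration or power for this outcome, so there is no figure to reproduce. The check asks how often an episode would be seen if only current symptoms are recorded.

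**Inputs from the protocol.** Postoperative visits at 1, 2, 3, 4, 6, 12 and 24 h, so the gaps after 4 h are 2, 6 and 12 h (20 h in total). Vomiting is listed only at 6, 12 and 24 h.

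**Assumptions.** One continuous episode of duration D per affected patient, onset uniform within the window, and a question about the present moment only.

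**Step 1: detection by frame.** For onset in a gap of length g that ends at a reading, detection = min(D, g)/g.

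| D | 0-4 h (nausea, pruritus) | 4-6 h | 6-12 h | 12-24 h |
|---|---|---|---|---|
| 1 h | 100% | 1/2 = 50% | 1/6 = 17% | 1/12 = 8% |
| 2 h | 100% | 100% | 2/6 = 33% | 2/12 = 17% |
| 4 h | 100% | 100% | 4/6 = 67% | 4/12 = 33% |
| 6 h | 100% | 100% | 100% | 6/12 = 50% |
| 12 h | 100% | 100% | 100% | 100% |

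At D = 0.5 h the 0-4 h figure falls to 50%.

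**Step 2: early vomiting.** With the first listed reading at 6 h, vomiting that starts uniformly in 0-4 h is seen only if it is still present at 6 h. The probability is (D - 2)/4, held between 0 and 1: 0% for D up to 2 h, 25% at 3 h, 50% at 4 h and 100% at 6 h.

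**Step 3: effect on a pooled 24 h pruritus rate.** For onset uniform over 4-24 h, the catch rate is c(D) = [min(D,2) + min(D,6) + min(D,12)]/20. This gives 0.15, 0.30, 0.50, 0.70 and 1.00 for D = 1, 2, 4, 6 and 12 h. Assume a true incidence of 50% in both arms, with 70% of hydromorphone and 30% of morphine episodes starting before 4 h. Neither figure is in the documents. Observed rate = 0.5 × [p + (1 - p) × c(D)], where p is the share starting before 4 h.

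| D, same in both arms | Hydromorphone | Morphine | Difference (points) |
|---|---|---|---|
| 1 h | 0.5 × (0.7 + 0.3 × 0.15) = 37.25% | 0.5 × (0.3 + 0.7 × 0.15) = 20.25% | 17 |
| 2 h | 39.5% | 25.5% | 14 |
| 4 h | 42.5% | 32.5% | 10 |
| 6 h | 45.5% | 39.5% | 6 |
| 12 h | 50% | 50% | 0 |

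Now let the durations differ, keeping hydromorphone at D = 2 h (39.5%). Morphine at D = 4 h gives 32.5% (7 points). At 6 h it gives 39.5% (no difference). At 12 h it gives 50% (reversed, by 10.5 points).

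**The case against.** The strongest objection is that the present-moment reading is an inference. Patients are asked about presence, and the text does not confine the answer to now. A question about vomiting makes most sense as a look-back. The frames after 4 h end at visit times, which fits interval questioning, and the attached sheet might settle the matter. This stands in part: the recall period is undefined, not shown to be wrong. The reference to time frames in outcome 5 does not fill the gap, because section 5(e) uses the same phrase for satisfaction, which Study Design collects only at the end of the procedure and at 24 h.

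A reader might also infer that the visits, dense early and sparse late, make hydromorphone look worse on side effects. The documents do not support that, for four reasons:

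- The different timing is reported for pruritus only, and after epidural rather than intrathecal use.
- For vomiting the argument fails and partly reverses, because the hourly visits do not list it.
- Outcome 5 is defined by frame and both arms have the same visits. With equal durations and uniform onset, detection within a frame is the same in both arms. A difference arises only in a rate pooled over 24 h, which outcome 5 does not specify.
- Its size and sign depend on durations. Background describes hydromorphone as shorter acting. If morphine's side effects also last longer, the difference shrinks, vanishes or reverses, as Step 3 shows.

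Nor can one say that the plan cannot give incidence at all. Recording during surgery is every 5 minutes, hourly visits catch any nausea or pruritus of 1 h or more that starts in 0-4 h, and long late episodes are caught.

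**Conclusion.** The concern holds as a gap in measurement. As written, the postoperative data do not define the onset and incidence that outcome 5 promises. If only current symptoms are recorded, short late episodes are missed: for onset in 12-24 h, detection runs from 8% (1 h) through 17%, 33% and 50% (2, 4 and 6 h) to 100% (12 h). Vomiting in the first 4 postoperative hours is not asked about until 6 h.

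Bias between the arms is a conditional possibility, limited to a pooled 24 h pruritus rate and to earlier onset with hydromorphone. The documents fix neither its size nor its direction.

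The percentages rest on assumed durations, uniform onset and the literal reading of presence. The missing look-back, start time and early vomiting question can be read from the text without any assumption. This is a secondary outcome and does not affect the primary fentanyl comparison.

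**What to change.** At every existing postoperative visit, including the four hourly ones, ask about any nausea, vomiting or itching since the last visit, with approximate start time, and also whether it is present now. Define secondary outcome 5 as any episode within the interval. At each visit, copy from the chart any antiemetic or antipruritic given since the last one. The frames begin at 1 h, so state where an episode reported at the 1 h visit is counted.

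If the attached sheet already asks about the interval, the protocol should say so and list vomiting at the hourly visits. Section 5(c) rules out protocol changes once the interim data have been analyzed, so this should be settled before then.

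The cost is a reworded sheet and outcome definition, with no added visits. The downside is some recall error over the 6 h and 12 h intervals. Apart from that, every interval from 0 to 24 h is covered whatever the episode length, and the difference in Step 3 that comes from visit timing disappears.

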The study design was described above. Every patient will receive a spinal anesthetic, as is standard of care for primary elective cesarean section. All standard anesthetic safety protocols and all standard nursing protocols will be followed. The only difference is the use of the study drug.

Every patient in this study will be given a pca for post-operative analgesia. The nurses in the post anesthesia care unit and post-partum unit are familiar with pca use and are capable of assessing the patients for sedation and respiratory depression. All cesarean section patients already have to be monitored for respiratory depression in the first 24 hours. The nurses are therefore equipped and qualified to monitor the study patients. The study patients will get the same monitoring as every cesarean section patient in the post-partum unit.

Data will be collected as described above. Only data up to 24 hours will be obtained.

g) Specimen Banking

This is not applicable to the current study.

h) Data Management and Confidentiality

 MOUNT SINAI SCHOOL OF MEDICINE	Protocol Title:	
	Principal Investigator:	
	Primary Contact Name/Contact Info	
	Date Revised:	
	Study Number:	

Data will be collected on paper that will indicate the patient's medical record and her study number assignment, and her initials. There will be no indication on these sheets of the patient's name. The data collection sheet is attached. The data on the sheets will be transferred to an Excel computerized spreadsheet without her initials. The excel data base is in a computer with a password. Also, the excel program is protected by a password. We will have a separate binder that will have the patients name along with her medical record # should we need to recheck records for any reason. The binder with the data sheet will be kept in the anesthesia research office (room KCC 840) that is kept locked at all times. The binder with the identifying information will be kept in the obstetric anesthesia office KP 2-58, also a locked office. Only the PI will have access to these records.

i) Provisions to Monitor the Data to Ensure the Safety of subjects

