17) Sharing of Results with Subjects

Results will not be shared with the patients or their obstetricians.

 MOUNT SINAI SCHOOL OF MEDICINE	Protocol Title:	
	Principal Investigator:	
	Primary Contact Name/Contact Info	
	Date Revised:	
	Study Number:	

18) IRB Review History

N/A

19) Control of Drugs, Biologics, or Devices

Note: The IDS has its own forms that must be completed and a review process that must be followed before the IDS representative will sign off on Appendix B for submission to the PPHS.

The Mount Sinai Labor and Delivery Unit utilizes a Pyxis machine, which stores and dispenses controlled substances. The pyxis is accessed by passcode and fingerprint. Currently the morphine used for cesarean section is stored in the pyxis and is accessed by identifying the patient and withdrawing the drug. The Pyxis records who took out the medication and the time of withdrawal. The hydromorphone will be stored in this secure pyxis machine as well.

References:

2. Rauch, E. "Intrathecal Hydromorphone for Postoperative Analgesia After Cesarean Delivery: A Retrospective Study". AANA Journal. 2012 Aug;80(4 Suppl):S25-32
3. Halpern, S.H et al. "Epidural Morphine vs. Hydromorphone in post-cesarean section patients". Canadian Journal of Anesthesia. 1996; 43(6):595-598.

Statistical plan

Categorical variables were tested via chi-square test, while continuous variables were tested via t-test, paired t-test, Wilcoxon rank sum test, or Mann-Whitney U test where applicable.

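### Section 5c fixes the total sample size only after a by-arm look at the primary outcome, with no re-sizing rule or error control, so type I error is not guaranteed

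*Combined protocol and SAP*

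**What the plan says.** Section 5c (Number of Subjects) explains that, without earlier comparative studies, "we cannot perform a power analysis to determine the number of patients required". It plans a first stage of 20 patients, 10 per group, and continues: "We will then perform an interim analysis of the data to see how much fentanyl is being used in the hydromorphone and morphine group". Then: "At that point we will determine the total number of patients required and inform the IRB and update the protocol accordingly". Its last sentence promises that nothing in the protocol will change once the data have been analysed.

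Section 5e makes the variable examined at the interim the primary one: "The primary outcome is total dose of fentanyl pca used in 24 hours".

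Section 4 gives a total: "The study will involve 50 patients scheduled for primary elective cesarean section". It does not derive this number, call it a maximum or connect it to Section 5c.

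The statistical plan is a single sentence. For continuous outcomes it says "continuous variables were tested via t-test, paired t-test, Wilcoxon rank sum test, or Mann-Whitney U test where applicable". It states no alpha, sidedness, interim adjustment or method of combining stages.

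**The concern.** A final test that treats N as fixed has its nominal error rate only if N did not depend on the treatment difference seen along the way. Here the difference on the primary outcome is on view when N is chosen, and no rule limits the choice. The true error rate then depends on an unwritten decision and may lie above or below nominal. A reader of the final p-value could not tell which, and could not exclude that N was chosen to suit the emerging result.

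The look is also unnecessary for its purpose. A trial is sized from a target difference and an SD. The target is a clinical judgement that can be made now. The SD can come from 20 patients without knowing who received which drug.

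**Working it through.** **Reproducing the plan's figure.** The 50 in Section 4 cannot be reproduced, because no alpha, power, difference or SD is given. For orientation, 25 per arm with a two-sided 5% t-test has 80% power for 0.81 SD (noncentral t). The normal approximation gives (1.96 + 0.8416) × √(2/25) = 0.79 SD.

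**Inputs from the documents.** First stage of 10 per arm; 1:1 allocation; 24-hour fentanyl as the outcome; unadjusted two-sample test; 50 patients mentioned in Section 4.

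**Assumptions.** Two-sided 5%, 80% power, no true difference, final t-test on all patients. Every rule, minimum and cap below is assumed. Re-sizing formula, rounded up:

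n per arm = 2 × (1.96 + 0.8416)² × s²/d² = 15.70 × s²/d²

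Here s is the SD and d is either the observed difference or a fixed target. With a 0.8 SD target, n = 15.70/0.64 = 24.5, so 25 per arm.

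**Simulated type I error.** Skewed means lognormal with log-SD 1.

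| How N is set | Limits (total) | Normal | Skewed, t-test |
|---|---|---|---|
| Fixed | 50 | 5.0% | 4.1% |
| Observed difference | 20 to 50 | 6.6% | 5.2% |
| Observed difference | 50 to 200 | 6.4% | 5.6% |
| Observed difference | 20 to 200 | 8.0% | 6.7% |
| Within-arm SD, 0.8 SD target | 20 to 200 | 5.7% | 4.5% |
| SD of all 20 combined, 0.8 SD target | 20 to 200 | 5.0% | 4.3% |

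For skewed doses the rank test gives 4.8% with N fixed and 5.6% to 6.7% under the observed-difference rules. The within-arm SD rule gives 5.2% (normal) with a minimum of 50, and 5.8% with a 1.0 SD target. Not every rule inflates the error: stopping at 20 whenever the observed difference would need more than 50 patients gives 3.5%.

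**Why the observed difference is a poor basis for N.** From 10 per arm its 95% margin is 2.101 × √(2/10) = 0.94 SD either way, which is larger than the 0.81 SD that 50 patients can detect with 80% power.

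**How stable N becomes.** True difference 0.8 SD, limits 10 to 100 per arm; n per arm:

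| Rule | Normal: IQR | Skewed: IQR |
|---|---|---|
| Observed difference | 12 to 62 | 10 to 34 |
| SD of all 20 combined | 23 to 35 | 12 to 30 |

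The combined-SD rule has a 95% range of 14 to 50 per arm with normal data. With skewed doses the range is 10 to 100, the assumed limits themselves. Its clear advantage in stability therefore holds only for roughly normal data.

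**The case against.** *The first 20 are handled blind.* The blinding phrase in Section 5c describes enrolment and data collection. The next sentence names both drug groups as the object of the interim analysis, and nothing says the data are viewed combined.

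*The protocol promises no change after the data are analysed.* This is the nearest thing to a safeguard in Section 5c. Read literally, it contradicts the commitment one sentence earlier to update the protocol with a new total. Read generously, it means that only N may move, which leaves N without a rule.

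*The total is 50.* If N stayed at exactly 50 with no early claim, the error rate would be held. But Section 5c leaves the total open. A cap alone does not suffice: 6.6% in the example above.

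*The effect may be small.* This stands. The text fits sizing on the within-arm SD as well as on the observed difference, and the former costs under one percentage point. Skewed doses shrink the inflation further.

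*An independent monitor exists.* Section 5i names one for data and safety monitoring but does not assign the interim analysis to that person.

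A reader might also infer from the record-access sentence in Section 5h that an unblinded PI will assess later patients. That sentence follows a description of data sheets and identity binders and says nothing about interim results, so it does not support this.

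**Conclusion.** The point holds and should be fixed: N is set after a by-arm look at the primary outcome, with no written rule and no error control. Confidence is medium because the size cannot be known from the documents. Under assumed rules at two-sided 5%, type I error runs from about 5% to about 8% with normal data if N is driven by the SD or the observed difference, and one conservative rule falls to 3.5%. These are examples, not bounds.

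Two stronger readings are tempting and not supported. One is that the trial's error rate is inflated to some stated figure such as 8%; that needs a rule based on the observed difference and wide limits, neither of which is written. The other is that sizing with arms not identified costs power in itself. Power follows the target. At a true 0.5 SD, with limits of 50 to 200 patients and normal data, a 0.8 SD target gives 46% and a 0.5 SD target about 78%, at a mean of about 133 patients. The observed-difference rule gives a nominal 79% at a mean of 126.

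**What to change.** Rewrite Section 5c as follows.

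1. Before any look, state alpha, sidedness, power and the smallest difference in 24-hour fentanyl (mcg) that matters.
2. After 20 patients, compute only the SD of all 20 values combined, with arms not identified. Say explicitly that this is not the within-arm pooled SD.
3. Set N by a prewritten formula with a minimum and a cap, and reconcile both with the 50 in Section 4.
4. State that N is the only item that may change, which removes the conflict inside Section 5c.
5. Produce no by-arm efficacy summary until the last patient is complete.

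Two alternatives work. One is to fix N at 50 whatever the first 20 show, with no early claim, accepting 80% power only for about 0.81 SD. The other is to keep the by-arm look with a prespecified re-sizing rule and combination test, carried out by someone outside the team that assesses patients. The independent monitor could be considered, but the task would have to be assigned.

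The cost is protocol wording. The combined-SD rule gives no early read of the arm difference. It also enlarges N somewhat when a true difference exists: at 0.8 SD the combined variance rises by 0.8²/4 × 20/19 = 0.168, about 17%. N remains imprecise, especially with skewed doses, so the minimum and cap matter and the target needs care. For the combination test under the observed-difference rule (50 to 200), nominal power at 0.5 SD falls from 79.3% to 75.8%. An unadjusted test held to a true 5% also gives 75.8%, so that loss only removes the inflated error.

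### Secondary outcomes 4 (satisfaction) and 5 (nausea, vomiting, pruritus) are defined over time frames for which the protocol's own visit schedule does not list all the readings

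*Combined protocol and SAP*

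**What the plan says.** Section 5(e), Study Endpoints, sets the frames under secondary outcome 2 (PCA use): "Between 1-4 hrs, 4-6 hrs, 6-12 hrs, 12-24 hrs". Outcomes 3 to 5 then reuse them. Outcome 4 is "Patient satisfaction scores in the above time frames". Outcome 5 is "Assessment of nausea and vomiting and pruritus in the above time frames", and its purpose is given as "This will help us understand the onset and incidence of these side effects among the two groups".

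The readings are scheduled in Section 5, Study Design:

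- **During surgery:** nausea, vomiting and pruritus are recorded every 5 minutes.
- **End of the procedure:** satisfaction is rated on a 1-5 scale.
- **First 4 hours:** "The patients will then be followed hourly for the first 4 hours by the investigating team". Pain scores are taken, and "The presence of nausea and pruritus will also be assessed at these time points". Vomiting is not named.
- **Later:** "The patients will then be visited again at 6hrs, 12 hrs, and 24 hrs". Pain, nausea, vomiting and pruritus are asked about. Satisfaction is not named in this list.
- **24 h:** a separate sentence adds an overall rating of satisfaction with pain control and the anesthetic experience.

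Section 5(d), Study Timelines, says "Each individual subject will be followed for 24 hours after cesarean section". Section 5(f) refers back to this description for data collection and adds no readings. Section 5(h) says that a data collection sheet is attached; it is not part of the text available for this review.

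**The concern.** An outcome defined by time frame needs at least one reading that belongs to each frame. If staff follow the protocol text as written, outcome 4 cannot be reported for the middle of the follow-up period, and whoever writes the report must decide afterwards what outcome 4 means.

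For outcome 5, the earliest postoperative frame has nausea and pruritus but no vomiting. That frame matters: outcome 5 is meant to show onset as well as incidence, and the Background section expects hydromorphone to act sooner and for a shorter time than morphine. Side effects are also one of the two questions that the Brief Summary gives as the reason for the trial.

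**Working it through.** No sample-size, power or alpha figure bears on this point. The check sets the schedule in Section 5 against the frames in Section 5(e).

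**Inputs.** Postoperative visits are at 1, 2, 3, 4, 6, 12 and 24 h, which is 4 + 3 = 7 visits. Pain, nausea and pruritus are listed at all 7. Vomiting is listed at 6, 12 and 24 h, so at 3 of 7. Satisfaction is listed at the end of the procedure and at 24 h.

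**Count.** Each visit on a boundary is assigned to the frame that it closes, and hours count from the end of surgery, as Section 5(d) suggests:

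| Item | 1-4 h | 4-6 h | 6-12 h | 12-24 h |
|---|---|---|---|---|
| Nausea, pruritus (each) | 4 | 1 | 1 | 1 |
| Vomiting | 0 | 1 | 1 | 1 |
| Satisfaction | 0 | 0 | 0 | 1 |

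**Do the zeros depend on the conventions?**

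- *Boundary rule.* The satisfaction readings fall at about 0 h and at 24 h, so no assignment of the 4, 6 or 12 h visits puts one into 4-6 or 6-12 h. The first postoperative vomiting reading is at 6 h, so no assignment puts one into 1-4 h.
- *Hour zero.* The protocol does not define it. If hours ran from the spinal injection and surgery ended after hour 1 (an assumption; no duration is given), the end-of-procedure satisfaction rating and some intraoperative vomiting readings would fall into 1-4 h by accident. Satisfaction in 4-6 and 6-12 h would still be empty, and the hourly visits would still not list vomiting.

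**What the existing readings can supply.**

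- The 24 h satisfaction item is an overall rating, so it is at best a proxy for 12-24 h.
- The look-back of the 6 h vomiting question is not stated. If it asks only about that moment, earlier vomiting is missed. If it covers everything since vomiting was last asked, earlier vomiting is counted but cannot be placed in 1-4 h or 4-6 h.

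**The case against.** The strongest reply concerns vomiting. The evidence is one missing word in one sentence. Vomiting is named during surgery and again at 6, 12 and 24 h, and the protocol elsewhere shortens the side-effect list to nausea and pruritus (Background; Potential Benefits). The intraoperative sentence is punctuated as if nausea and vomiting were one item, and on that reading outcome 5 has data in every frame. This largely stands: the omission is probably a slip. It does not settle the matter, because vomiting is listed separately from nausea at the later visits. If outcome 5 were a composite, 1-4 h would hold nausea alone and later frames nausea plus vomiting, so the frames would not be comparable with each other.

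The second reply is that the data sheet is part of the plan and may already carry these items. This also stands as a limit. A reader might infer that the readings will not be taken and that outcome 4 is lost for the middle frames whatever happens. The documents do not support that inference. They show that two sections of the protocol text disagree; what staff would actually record is unknown without the sheet.

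A reader might also infer that the side-effect comparison as a whole is compromised. It is not: nausea and pruritus each have seven scheduled postoperative readings, with at least one in every frame under the count above. Satisfaction is still measured twice. What fails for outcome 4 is mainly the phrase about time frames, carried over from the PCA outcome.

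**Conclusion.** The protocol text contradicts itself on two of its five secondary outcomes.

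- **Outcome 4:** no scheduled satisfaction reading in 4-6 and 6-12 h, and none in 1-4 h if hours count from the end of surgery. This is the firmer half.
- **Outcome 5:** no scheduled postoperative vomiting reading in 1-4 h, probably through a dropped word.

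The mismatch in the text is certain. Loss of data is not, since it depends on the unseen data sheet. Importance is low: the primary outcome (24 h fentanyl PCA dose), PCA timing, pain, nausea and pruritus are unaffected, and wording can reconcile the sections.

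**What to change.** 1. In Section 5, add vomiting to the sentence on the hourly visits in the first 4 hours, so that it matches the later visits and outcome 5.
2. In Section 5(e), restate outcome 4 as satisfaction at the end of the procedure and overall satisfaction at 24 h, dropping the reference to the four frames.
3. Check the attached data sheet against both sections and make all three agree.

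The cost is a wording edit, plus a line on the sheet if vomiting is not already there for hours 1 to 4. No visit is added and no treatment changes. The edit belongs before the interim analysis, because Section 5(c) rules out protocol changes once data have been analyzed. If collection is already complete, outcome 4 can still be reported at the two times actually collected, with the departure from the stated frames disclosed.
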